### **12.2 Analysis Data Sets**

Subjects who receive study treatment will be included in the safety analyses.

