## 12.4 Safety

Safety data will be summarized by dose group and based on their initial dose level or treatment group (i.e., if a dose reduction occurs, they will be considered in their initial group). Descriptive statistics will be provided for actual values and change from baseline values for vital signs, weight, blood parameters, ECG (QT).

AE assessment and treatment area evaluation including, but not limited to evaluation of edema, bruising, dysphasia, dysphonia, erythema, dyspigmentation, induration, numbness, pain, paresthesia, and pruritus.

The incidence and severity of AEs reported during the study and their relationship to study drug will be tabulated. AEs will be coded using MedDRA™ and will be presented by body system. AEs will be graded according to the Common Terminology Criteria for Adverse Events (CTCAE) v 5.0 (Table 5).

The World Health Organization Drug Dictionary (WHODD) will be used to classify prior and concomitant medications by therapeutic class and preferred term. Prior and concomitant medication usage will be summarized by the number and percentage of subjects receiving each medication within each therapeutic class by dose cohort.

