For the primary endpoint (proportion of high dose group subjects who have at least a 1-grade improvement from baseline to Day 84 on the C-CAT scale), the assumed true rates are 70% in the RZL-012 high dose group and 35% in the placebo group (a difference of 35 percentage points). Based on the use of a two-sided test of equality of binomial proportions at the alpha=0.05 level of significance, 41 subjects per group are required at 90% power. In order to account for a dropout rate of up to ~9%, the planned sample size is 45 subjects per group, for a total sample size of 135 subjects.

- **Statistical Analysis Software and Data Management**

Data manipulation, tabulation of descriptive statistics, calculation of inferential statistics, and graphical representations will be performed using SAS® version 9.4 or higher for Windows. If the use of other software is warranted, the final statistical methodology report will detail what software was used for what purposes.

- **Data Management**

Data management for the study is performed by Medistat.

- **Medical Coding**

Concomitant medications entered into the database are coded using the WHO (World Health Organization) Drug Public Website Dictionary named WHOCC-ATC/DDD index, which employs the Anatomical Therapeutic Chemical classification system.

Adverse events are coded using the most updated version of Medical Dictionary for Regulatory Activities (MedDRA) terminology.

Medical history events are coded using the most updated version of Medical Dictionary for Regulatory Activities (MedDRA) terminology.

- **Handling of Missing data**

Every effort will be made to obtain all data from all subjects who have been enrolled, to minimize missing data.

A subject with missing primary endpoint data will be imputed as treatment failure.

- **Subject Population for analyses**

MediStat Statistics in Medicine	DOCUMENT NUMBER: 140-BST-PLN-001	PAGE: 13 of 16
TITLE: Statistical Analysis Plan of Protocol Number RZL-012-SMF-P2bUS-001	EFFECTIVE DATE : 08/03/2022 REVISION NUMBER : 1.0	

The Intent-to-treat population (ITT) will consist of all enrolled subjects who received the study treatment, (exposed population), including subjects prematurely withdrawn. The ITT population will serve as the principal data analysis set for analyses of efficacy and safety endpoints. Subjects will be analyzed according to the treatment received

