The Per-Protocol population (PP) will consist of all subject included in the ITT population who were rated for both S-CAT and C-CAT on both baseline and day 84 visits. The PP population will serve as a sensitivity analysis of the efficacy endpoints.

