## 6. STATISTICAL ANALYSIS

- General

All measured variables and derived parameters will be listed individually and, if appropriate, tabulated by descriptive statistics.

For categorical variables, summary tables will be provided giving sample size, absolute and relative frequency and 95% CI (Confidence Interval) for proportions by study group.

For continuous variables, summary tables will be provided giving sample size, arithmetic mean, standard deviation, coefficient of variation (CV%), median, minimum and maximum and 95% CI (Confidence Interval) for means of variables by study group.

All tests will be two-tailed, and a p value of 5% or less will be considered statistically significant.

The data will be analyzed using the SAS ® version 9.4 (SAS Institute, Cary North Carolina).

Statistical methods presented in the SAP may be slightly different from those that are presented in the protocol. Differences are clearly stated and the SAP supersedes the protocol only with regard to the way data will be handled and analysed.

- Subject Disposition

A detailed description of subject accountability including count of subjects included, exposed, completed (i.e., subjects who complete the study treatment) and discontinued along with the main reason for discontinuation will be generated for each treatment group and for all subjects. All withdrawals from the study, taking place on or after study drug injection, will be fully documented in the body of the Clinical Study Report.

Demographic and Baseline Characteristics

MediStat Statistics in Medicine	DOCUMENT NUMBER: 140-BST-PLN-001	PAGE: 14 of 16
TITLE: Statistical Analysis Plan of Protocol Number RZL-012-SMF-P2bUS-001	EFFECTIVE DATE : 08/03/2022 REVISION NUMBER : 1.0	

Baseline will be defined as the last available and evaluable parameter value before and closest to the injection. If a rechecked value is used for baseline, it should be collected under the same conditions as for the planned baseline.

Baseline safety data will be presented along with subsequent safety values assessed during or after dosing.

- **Analysis of Efficacy for Primary Endpoint**

The proportion of subjects who have at least a 1-grade improvement in the C-CAT on Day 84 versus baseline will be calculated for the placebo group and the RZL-012 high-dose group along with 95% Confidence interval for proportion.

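### The SAP's intention-to-treat set is grouped by treatment received, so the primary test would not keep the randomised arms if a subject were injected from the wrong kit

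*SAP*

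**What the plan says.** Three statements in SAP section 5, Subject Population for analyses, fix the primary analysis set.

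- Membership: "The Intent-to-treat population (ITT) will consist of all enrolled subjects who received the study treatment, (exposed population), including subjects prematurely withdrawn".
- Role: "The ITT population will serve as the principal data analysis set for analyses of efficacy and safety endpoints".
- Grouping: "Subjects will be analyzed according to the treatment received". This sentence is not limited to safety.

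The only other efficacy set is a subset of this one: "The Per-Protocol population (PP) will consist of all subject included in the ITT population who were rated for both S-CAT and C-CAT" at both baseline and Day 84. It has no grouping rule of its own.

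SAP section 6 tests high dose against placebo by chi-square on the Day 84 C-CAT responder rate. It does not say whether those groups are as assigned or as received.

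Protocol 12.2 defines no efficacy set. Its whole content is: "Subjects who receive study treatment will be included in the safety analyses". Protocol 12.4 gives a grouping rule for safety only: "Safety data will be summarized by dose group and based on their initial dose level or treatment group", explained by the example of a dose reduction. On any conflict over analysis, SAP section 6 states that "the SAP supersedes the protocol only with regard to the way data will be handled and analysed".

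**The concern.** Intention-to-treat analysis keeps each subject in the arm chosen by the randomisation, because that comparison is protected from whatever determines the treatment actually given. The SAP uses the name but applies an as-treated rule. As written, a misallocated subject moves between numerators and denominators in the primary test, and readers of the report would take the result for a comparison of randomised arms. The per-protocol analysis cannot reveal the problem, since it is drawn from the same population.

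The route is narrow. Each subject has one treatment session and the supplies are blinded, so a dispensing error is essentially the only way for assigned and received treatment to differ. The rule exists for that event and needs to be right before unblinding. Changing it once an error is known would look data-driven.

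**Working it through.** **Inputs.** SAP section 5: 70% high dose, 35% placebo, two-sided alpha 0.05, 90% power, 41 per group required, 45 planned, missing primary data counted as failure. SAP section 6: chi-square test, high dose versus placebo. The documents give no misallocation rate. All responder counts below, and the high-dose rates of 60%, 55% and 35%, are assumptions.

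**1. The plan's own figure.** With pooled variance under the null and mean rate 0.525:

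n = [1.960·√(2·0.525·0.475) + 1.282·√(0.70·0.30 + 0.35·0.65)]² / 0.35² = 40.7, so 41 per group.

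This matches the SAP. The margin from 41 to 45 allows 1 − 41/45 = 8.9% dropout, which fits the stated figure of about 9%. The grouping rule does not enter this calculation.

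**2. Is there an as-randomised efficacy analysis anywhere?** SAP section 5 says treatment received. SAP section 6 names the groups without a rule. The per-protocol set is a subset of the same population. Protocol 12.2 and 12.4 concern safety. There is none.

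**3. What one misallocated subject does.** Pearson chi-square without continuity correction, with z = (a/n₁ − b/n₂) / √[p̄(1 − p̄)(1/n₁ + 1/n₂)], where p̄ is the pooled rate.

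First row in full:
- As randomised: 25/45 = 0.556, 16/45 = 0.356, p̄ = 41/90 = 0.456. z = 0.200/0.1050 = 1.905, p = 0.057.
- One placebo-randomised responder had received high dose, as treated: 26/46 = 0.565, 15/44 = 0.341. z = 0.2243/0.1050 = 2.136, p = 0.033.

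| Error | As randomised | p | As treated | p |
|---|---|---|---|---|
| One placebo-arm responder got high dose | 25/45 v 16/45 | 0.057 | 26/46 v 15/44 | 0.033 |
| One high-dose-arm responder got placebo | 26/45 v 16/45 | 0.035 | 25/44 v 17/46 | 0.059 |
| One high-dose-arm responder got placebo | 32/45 v 16/45 | 0.0007 | 31/44 v 17/46 | 0.0015 |
| Two high-dose-arm responders got placebo | 32/45 v 16/45 | 0.0007 | 30/43 v 18/47 | 0.0028 |

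The first two rows were chosen to lie near the 0.05 boundary, and there the conclusion changes, once in each direction. The last two lie near the planned rates, and there it does not.

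**4. How often the two groupings disagree, given exactly one error.** Exact binomial enumeration with 45 randomised per arm, the misallocated subject responding at the rate of the treatment received:

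| True rates (high v placebo) | Placebo to high dose | High dose to placebo |
|---|---|---|
| 70% v 35% (plan) | 3.3% | 3.4% |
| 60% v 35% | 8.1% | 8.0% |
| 55% v 35% | 8.6% | 8.3% |
| 35% v 35% | 2.4% | 2.4% |

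At the planned rates, the 3.3% splits into 2.3% where only the as-treated test is significant and 1.0% where only the as-randomised test is.

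**The case against.** The strongest reply is that this is a labelling defect with a remote consequence.

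- **Errors are unlikely.** Vials are assigned to each subject (protocol 8.5) and opened vials are not used for anyone else (10.4). Dispensing logs are reviewed at each monitoring visit (10.6), and case report forms are fully source verified (13.2).
- **The unconditional risk is small.** The 3.3% assumes that an error has occurred. If the chance of one high-dose/placebo error in the whole trial were 5 to 20% (an assumption), the risk at the planned rates would be 0.05 × 3.3% to 0.20 × 3.3%, about 0.2 to 0.7%.
- **No bias is shown.** With both arms at 35% and one error, the exact rejection rate is 5.3% as randomised and 5.0% as treated, so type I error is not inflated. As-treated grouping also keeps the 35-point difference and 92.7% power at 45 per arm. As-randomised grouping falls to 90.2% with one high-dose/placebo swapped pair and 87.0% with two.
- **The rule is open.** The SAP states that the set is the exposed population and how it is grouped.

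The points on rarity and on the boundary examples stand and limit the size of the concern. The type I error and power results hold only if misallocation is unrelated to prognosis. Blinding makes that plausible, but as-randomised grouping does not need the assumption. Stating the rule in the SAP does not help a reader of the report, who sees only the ITT label. Restricting the set to injected subjects is not at issue: assignment is disclosed immediately before injection (protocol 8.3), so few randomised subjects should go untreated.

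**Conclusion.** The concern holds. The SAP states a grouping rule that is wrong for a primary test presented as intention-to-treat, and nothing in either document supplies the as-randomised analysis. It should be fixed before unblinding.

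The size is contingent. Without a kit error, results are identical. With exactly one error between high dose and placebo, the significance call changes in about 3% of trials at the planned rates and 8 to 9% at the smaller assumed effects. A single subject can decide a borderline result, but a result near the planned 35-point difference is very unlikely to be overturned. The figures assume 45 randomised per arm, no missing data, and a misallocated subject who responds at the rate of the treatment received. The likelihood of an error is unknown from the documents.

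**What to change.** Replace the grouping sentence in SAP section 5 with wording to this effect:

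*Efficacy: all randomised and injected subjects (modified ITT) are analysed in the arm to which they were randomised, with a missing Day 84 C-CAT counted as treatment failure. Safety: all injected subjects are analysed according to the treatment they received.*

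Using all randomised subjects for efficacy would be equally sound; the SAP should name one. In addition:

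- derive the per-protocol set from the as-randomised efficacy set;
- keep an as-treated efficacy analysis, if wanted, as a sensitivity analysis only;
- align protocol 12.2 and 12.4 with the SAP, since 12.4 groups safety data by initial group and the SAP groups them by treatment received.

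The cost is SAP wording and a matching protocol clarification. It needs no new data or extra subjects, the planned 45 per group stands, and results are the same if no kit is misallocated.

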## 6. STATISTICAL ANALYSIS

- General

All measured variables and derived parameters will be listed individually and, if appropriate, tabulated by descriptive statistics.

For categorical variables, summary tables will be provided giving sample size, absolute and relative frequency and 95% CI (Confidence Interval) for proportions by study group.

For continuous variables, summary tables will be provided giving sample size, arithmetic mean, standard deviation, coefficient of variation (CV%), median, minimum and maximum and 95% CI (Confidence Interval) for means of variables by study group.

All tests will be two-tailed, and a p value of 5% or less will be considered statistically significant.

The data will be analyzed using the SAS ® version 9.4 (SAS Institute, Cary North Carolina).

Statistical methods presented in the SAP may be slightly different from those that are presented in the protocol. Differences are clearly stated and the SAP supersedes the protocol only with regard to the way data will be handled and analysed.

- Subject Disposition

A detailed description of subject accountability including count of subjects included, exposed, completed (i.e., subjects who complete the study treatment) and discontinued along with the main reason for discontinuation will be generated for each treatment group and for all subjects. All withdrawals from the study, taking place on or after study drug injection, will be fully documented in the body of the Clinical Study Report.

Demographic and Baseline Characteristics

MediStat Statistics in Medicine	DOCUMENT NUMBER: 140-BST-PLN-001	PAGE: 14 of 16
TITLE: Statistical Analysis Plan of Protocol Number RZL-012-SMF-P2bUS-001	EFFECTIVE DATE : 08/03/2022 REVISION NUMBER : 1.0	

Baseline will be defined as the last available and evaluable parameter value before and closest to the injection. If a rechecked value is used for baseline, it should be collected under the same conditions as for the planned baseline.

Baseline safety data will be presented along with subsequent safety values assessed during or after dosing.

- **Analysis of Efficacy for Primary Endpoint**

The proportion of subjects who have at least a 1-grade improvement in the C-CAT on Day 84 versus baseline will be calculated for the placebo group and the RZL-012 high-dose group along with 95% Confidence interval for proportion.

The Chi-Square test will be applied to test the statistical difference between the placebo group and the RZL-012 high-dose group in responder rate at Day 84. Responder rate is defined as the percentage of subject achieving at least a 1-grade improvement from baseline in C-CAT.

- **Analysis of secondary Endpoints**

Secondary endpoints (improvement in 1 point in S-CAT and C-CAT, improvement in 2 points in both S-CAT and C-CAT) will be tested using a two-sided test of equality of binomial proportions at the alpha=0.05 level of significance.

All other secondary endpoints will be tested using a two-sided test at the alpha=0.05 level of significance.

- The Chi-Square test will be applied to test the statistical difference between the placebo group and each of the RZL-012 dose groups in the responder rate at Day 84 where responder rate is defined as the percentage of subject achieving at least a 1-grade improvement from baseline in both S-CAT and C-CAT.
- The change and percentage of change from baseline at Day 84 in SMF thickness measured with caliper and in SMF volume by MRI will be calculated along with 95% Confidence intervals.

The Paired T-test for two means (paired observations) will be applied for testing the statistical significance of the change and percentage of change from baseline at Day 84 in SMF thickness measured with caliper and in SMF volume by MRI within each study group.

MediStat Statistics in Medicine	DOCUMENT NUMBER: 140-BST-PLN-001	PAGE: 15 of 16
TITLE: Statistical Analysis Plan of Protocol Number RZL-012-SMF-P2bUS-001	EFFECTIVE DATE : 08/03/2022 REVISION NUMBER : 1.0	

The two-sample T-test for independent samples will be applied for testing the statistical significance of the change and percentage of change from baseline at Day 84 in SMF thickness measured with caliper and in SMF volume by MRI between each of the RZL-012 dose groups and the placebo group.

- Analysis of Exploratory endpoint
  - SMF improvement

The SMF improvement using the Global Aesthetic Improvement Scale (GAIS) , the physician Global Assessment of Change Scale, Subjects Global Self-Assessment of Change Scale, Subject Global Assessment of Change Scale, the subject's satisfaction questionnaires, and the subjects's impact questionnaire will be summarized at each timepoint and by treatment group.

- Analysis of Safety

Safety data from the study will be summarized descriptively by treatment. The incidence of AEs will be presented by treatment.

Descriptive statistics will be calculated for quantitative data and frequency counts and percentages will be provided for categorical data. The nature, frequency, seriousness, severity and relation of AEs to study treatment will be tabulated for all subjects combined and by treatment.

Change-from-baseline values for vital signs, clinical laboratory and ECG will be summarized. Serious adverse events (SAEs) will be described in narratives as part of the study report.

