### Primary Endpoint

Comparison of the proportion of subjects who have at least a 1-grade improvement in the C-CAT on Day 84 versus baseline between the RZL-012 high dose (270 mg/5.4 mL) group and the placebo group.

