### Secondary Endpoints:

MediStat Statistics in Medicine	DOCUMENT NUMBER: 140-BST-PLN-001	PAGE: 9 of 16
TITLE: Statistical Analysis Plan of Protocol Number RZL-012-SMF-P2bUS-001	EFFECTIVE DATE : 08/03/2022 REVISION NUMBER : 1.0	

- Proportion of subjects who have at least a 1-grade improvement in both the C-CAT and S-CAT (Day 84 versus baseline) in the RZL-012 groups versus placebo group.
- Proportion of subjects who have at least a 2-grade improvement in both the C-CAT and S-CAT (Day 84 versus baseline) in the RZL-012 groups versus placebo group.
- Reduction in SMF volume by MRI (Day 84 versus screening) in the RZL-012 groups versus placebo group.
- Reduction in SMF thickness measured with caliper (Day 84 versus baseline) in the RZL-012 groups versus placebo group. Safety assessment of RZL-012 in the treatment of SMF reduction.
- safety of RZL-012 in the treatment of SMF reduction.

Exploratory endpoints:

- Physicians Global Assessment
- SMF improvement using the Global Aesthetic Improvement Scale (GAIS).
- Subject Global Self-Assessment
- SMF improvement using the Subject Global Assessment of Change Scale.
- SMF improvement using the subject's satisfaction questionnaires.
- SMF improvement using Subject's impact questionnaire.

- Study Design

This is a Phase 2b, double-blind, randomized, three-arm, placebo-controlled study that consists of a screening period, baseline period, and a randomized treatment period. Subjects receive a single treatment session that consists of multiple injections of RZL-012 or placebo into the submental area under the chin, after which they are monitored for safety and efficacy over 84 days.

Following the completion of Day 84 visit of the last subject, subjects from three (3) chosen clinical sites are followed up to a 1 year after injection to evaluate the long term safety and efficacy. The additional follow up visits are conducted at 6 and 12 months after injection.

Study participants are adult volunteers (135 subjects - 45 subjects per group) of 18 to 65 years of age who have consented to participate in this study. Each subject is randomized to either active treatment (high or low dose RZL-012) or placebo at a ratio of 1:1:1 per group and receives one of the following:

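### The primary comparison of high dose with placebo has no pre-specified difference with a confidence interval, and the baseline C-CAT grade already collected is not used

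*SAP*

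**What the plan says.** The primary endpoint in SAP section 5 is a contrast of the high-dose arm with placebo; its definition begins "Comparison of the proportion of subjects who have at least a 1-grade improvement in the C-CAT on Day 84 versus baseline between the RZL-012 high". Protocol section 2.3.1 agrees. The sample size rationale also rests on a contrast, 70% against 35%, and on a "two-sided test of equality of binomial proportions at the alpha=0.05 level of significance".

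For the result itself, SAP section 6 (Analysis of Efficacy for Primary Endpoint) plans two outputs. One is the responder proportion in each of the two groups "along with 95% Confidence interval for proportion". The other is a p-value: "The Chi-Square test will be applied to test the statistical difference between the placebo group and the RZL-012 high-dose group". The general rule in the same section gives intervals for proportions group by group. Protocol section 12.3 and the synopsis plan the same: intervals by arm and a Pearson chi-square test.

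Neither document names a risk difference, risk ratio or odds ratio for this endpoint, or an interval for one. The per-protocol sensitivity analysis names no effect measure, and the responder composites of C-CAT and S-CAT are likewise assigned only a test. Entry requires C-CAT grade 3 or 4 (protocol section 3.1), and the grade is rated again on Day 0 before injection (section 8.2). No analysis uses it as a stratum or covariate.

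**The concern.** The quantity that the trial was sized to detect has no planned estimate of its own. A p-value does not show how large or how small the benefit could plausibly be, and two separate intervals answer a different question from an interval for their difference. For a Phase 2b trial with two active doses, the size of the effect over placebo and its precision are natural things to carry forward. If the interval is added at the reporting stage, its method is picked with the data in view.

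Baseline grade is a two-level factor rated before treatment in every subject. If response depends on starting grade, ignoring it gives up a little precision that costs nothing to keep.

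**Working it through.** **Inputs.** From SAP section 5: planning rates 0.70 and 0.35; two-sided alpha 0.05; "41 subjects per group are required at 90% power"; 45 per group after dropout; equal allocation. The example counts below are illustrations, not trial data.

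**1. The plan's own figure.** With pooled variance under the null and no continuity correction, the mean rate is 0.525 and

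n = [1.960·√(2·0.525·0.475) + 1.282·√(0.70·0.30 + 0.35·0.65)]² / 0.35² = (1.384 + 0.848)² / 0.1225 ≈ 40.7, so 41 per group.

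Power at 41 is 0.902. Allowing for dropout, 41/(1 − 4/45) = 45, and 4/45 = 8.9%, which fits the stated figure of about 9%. The sample size stands.

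**2. The missing interval at the planning rates.** A Wald interval with 45 per group is 0.35 ± 1.960·√(0.70·0.30/45 + 0.35·0.65/45) = 0.35 ± 0.193, or 0.157 to 0.543.

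The nearest whole counts are taken as 32/45 and 16/45. The Wilson intervals by arm are 0.566 to 0.823 (around 0.711) and 0.232 to 0.502 (around 0.356). Newcombe's method combines them around the difference d = 0.356:

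- lower limit: 0.356 − √[(0.711 − 0.566)² + (0.502 − 0.356)²] = 0.356 − 0.206 = 0.150
- upper limit: 0.356 + √[(0.823 − 0.711)² + (0.356 − 0.232)²] = 0.356 + 0.166 = 0.522

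The interval is about 15 to 52 points, beside a Pearson p-value of 0.0007.

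**3. Does the method matter?** For the same counts, the Wald interval is 16.3 to 54.8 points and Newcombe's is 15.0 to 52.2. The gap is small, but it is a choice that should be made beforehand.

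**4. Do the arm intervals stand in for the contrast?**

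| High dose | Placebo | Wilson 95%, high dose | Wilson 95%, placebo | Pearson p | Difference in points (Newcombe 95%) |
|---|---|---|---|---|---|
| 32/45 | 16/45 | 57–82% | 23–50% | 0.0007 | 36 (15 to 52) |
| 26/45 | 16/45 | 43–71% | 23–50% | 0.035 | 22 (2 to 40) |
| 25/45 | 16/45 | 41–69% | 23–50% | 0.057 | 20 (−0.5 to 38) |

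At the planning effect the arm intervals are well apart. In the second row they overlap although the test is significant, so they cannot be read as a test of the difference. In all three rows the unstratified Newcombe interval agrees with the unstratified chi-square test.

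**5. What stratifying by baseline grade could add.** The documents give neither the split between grades 3 and 4 nor any link between grade and response, so this rests on assumptions. In a simulation with half the subjects in each grade, stratification costs essentially nothing if grade is unrelated to response. It adds about 1 to 3 points of power if the responder rate differs by 20 to 30 points between grades.

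**The case against.** The best defence is that nothing is lost for good. The planned tables report group sizes and counts, and step 2 shows that these are enough for an unadjusted difference and its interval. A reader might infer that the trial can never estimate its effect with uncertainty; the documents do not support that. What is missing is the advance commitment to an estimate and a method.

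A reader might also infer that overlapping arm intervals would contradict a significant p-value. They would not: overlap of two separate intervals is not a test of the difference, and none occurs at the planning rates. Nor is the unadjusted test a fault. The documents name no stratification factor for the randomization, so an unstratified chi-square test breaches nothing and matches the test used for sizing.

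Sizing a later trial is not a stated objective, and this trial was itself sized from two arm-level rates, which the planned output will supply. That weakens any claim that later planning would be blocked.

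Finally, a stratified interval beside an unstratified p-value could disagree with it near the threshold. This objection stands and shapes the fix: interval and test must be matched.

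**Conclusion.** The point holds as a free improvement. The primary endpoint is a contrast, and no interval for that contrast is pre-specified in either document. The chi-square test, its type I error and the sample size of 41 (45 planned) per group are sound as they are.

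The size of what goes unreported is an interval of about 15 to 52 points, assuming 45 per arm and observed counts close to the planning rates. The possible gain from using baseline grade is small, 1 to 3 points of power, and depends on an even grade split and a clear link between grade and response, neither of which the documents give. The case for adding the difference and its interval does not depend on that gain.

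**What to change.** In SAP section 6, name the high-dose minus placebo risk difference with a 95% interval as the primary estimate, in the SAP's ITT set with missing primary data counted as failure, and state the interval method. Then choose one matched pair:

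- **Preferred:** the Mantel-Haenszel risk difference stratified by baseline C-CAT grade (baseline as the SAP defines it), with the Cochran-Mantel-Haenszel test as the primary test.
- **If the unstratified Pearson chi-square stays primary:** an unstratified difference with a Newcombe or Miettinen-Nurminen interval, and the stratified difference as supportive.

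Report the same estimate and interval for the C-CAT and S-CAT responder composites, for each dose against placebo. The cost is a sentence or two in the SAP, settled before unblinding, and an extra table column. If the stratified test becomes primary, the SAP should record this as a change from the protocol's Pearson test. Sample size, alpha and data collection do not change.
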